4.2.5.8 Exposure

Duration of exposure will be summarised for the SAF. The following summaries will be produced:

- Total exposure and actual exposure of savolitinib and osimertinib
- Exposure plot over time showing a line for each treatment arm
- Summary statistics (mean, standard deviation, median, quartiles, minimum, maximum) of RDI of savolitinib and osimertinib
- Summary of dose interruptions and reductions, with reasons, of savolitinib, osimertinib and placebo separately for the first 6 weeks and at any time (see Section 3.3.1 for details of analysis of missed or forgotten doses)
- Cumulative exposure over time, showing the number and percentage of patients treated for at least 0, 6 and 12 months
- Total number of treatment cycles received.

The calculation of exposure is given in Section 3.3.1.

Analysis methods for relative dose intensity

Summary statistics (mean, standard deviation, median, quartiles, minimum, maximum) will be presented for dose intensity.

4.2.6 Demographics and baseline characteristics

The following will be summarised for all patients in the FAS (unless otherwise specified) by treatment group and biomarker group:

- Patient disposition (including screening failures and reason for screening failure)
- Important protocol deviations
- Inclusion in analysis sets
- Demographics (age, age group [< 40 , $\geq 40 - < 65$, $\geq 65 - < 75$ and ≥ 75 years], sex, race, ethnicity, and country)

- Patient characteristics at baseline (height, weight)
- Previous disease-related treatment modalities
- Number of prior regimens of previous chemotherapy prior to this study
- Disease characteristics at baseline (ECOG performance status, primary tumour location, histology type, tumour grade, overall disease classification, FISH allocation status, prior lines of therapy, and immediate prior line of therapy)
- Extent of disease at baseline
- Disease related medical history (past and current)
- Relevant surgical history
- Disallowed concomitant medications
- Allowed concomitant medications
- Post-discontinuation cancer therapy
- Nicotine use, categorised (never, current, former).

The medications will be coded following WHO Drug dictionary.

4.2.7 Concomitant and other treatments

Information on any treatment within the four weeks prior to initiation of study drug and all concomitant treatments given up to 28 days after discontinuation of study treatment, or objective disease progression (whichever is later), with reasons for the treatment, will be recorded in the eCRF. Thereafter, only subsequent regimens of anti-cancer therapy will be recorded in eCRF.

Other anti-cancer therapies, investigational agents, and radiotherapy should not be given while the patient is on study drug.

Medications received prior to, concomitantly, or post-treatment will be coded using the AstraZeneca Drug Dictionary Anatomical Therapeutic Chemical (ATC) Classification codes. Concomitant medications will be summarised for the FAS by ATC classification codes.

For the purpose of inclusion in prior and/or concomitant medication or therapy summaries, incomplete medication or radiotherapy start and stop dates will be imputed as detailed in Section [4.2.5.1](#).

Prior medications, concomitant and post-randomised treatment medications are defined based on imputed start and stop dates as follows:

- Prior medications are those taken prior to study treatment with a stop date prior to the first dose of study treatment.
- Concomitant medications are those with a stop date on or after the first dose date of study treatment (and could have started prior to or during treatment).

- Post-treatment medications are those with a start date after the last dose date of study treatment.

In addition, all post-treatment anti-cancer medications and surgical procedures will be summarised for the full analysis set.

The following summaries will be produced:

- Summary of prior medications
- Summary of concomitant medications
- Summary of post study treatment cancer therapies.

All concomitant and other treatment data will be listed.

Missing coding terms should be listed and summarised as "Not coded".

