- Baseline for safety assessments will generally be the last value obtained prior to the first dose of study medication). Alternatively, if two visits are equally eligible to assess patient status at baseline (e.g., screening and baseline assessments both on the same date prior to first dose with no washout or other intervention in the screening period), the average can be taken as a baseline value. For non-numeric laboratory tests (i.e. some of the urinalysis parameters) where taking an average is not possible then the best value would be taken as baseline as this is the most conservative. In the scenario where there are two assessments on day 1, one with time recorded and the other without time recorded, the one with time recorded would be selected as baseline. Where safety data are summarised over time, study day will be calculated in relation to date of first treatment.
- Per Section 9.4.3 of the CSP, adverse events occurring in the savolitinib in combination with placebo group will be split into two presentations based on whether they occurred before or after cross-over.

Missing safety data will generally not be imputed. However, safety assessment values of the form of “< x” (i.e. below the lower limit of quantification) or > x (i.e. above the upper limit of quantification) will be imputed as “x” in the calculation of summary statistics but displayed as “< x” or “> x” in the listings. Additionally, adverse events that have missing causality (after data querying) will be assumed to be related to study drug.

Furthermore:

- For missing diagnostic dates, if day and/or month are missing, use 01 and/or Jan. If year is missing, put the complete date to missing.
- For missing AE start dates, the following will be applied:
 - a. Missing day: impute the 1st of the month unless month is the same as month of the first dose of study drug then impute first dose date
 - b. Missing day and month: impute 1st January unless year is the same as first dose date then impute first dose date
 - c. Completely missing: impute first dose date unless the end date suggests it could have started prior to this in which case impute the 1st January of the same year as the end date

When imputing a start date ensure that the new imputed date is sensible e.g. is prior to the end date of the AE.

- For missing AE end dates, the following will be applied:

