- a. Missing day: impute the last day of the month unless month is the same as month of the last dose of study drug then impute last dose date.
- b. Missing day and month: impute 31st December unless year is the same as last dose date then impute last dose date.

Flags will be retained in the database indicating where any programmatic imputation has been applied, and in such cases, any durations would not be calculated.

- If a patient is known to have died where only a partial death date is available, then the date of death will be imputed as the latest of the last date known to be alive + 1 from the database and the death date using the available information provided:
 - c. For Missing day only: using the 1st of the month
 - d. For Missing day and Month: using the 1st of January

With the exception of exposure data, safety data will not be summarised by biomarker group.

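### SAP 4.2.7 classifies medications from dates imputed by adverse-event rules, so partial dates can place next-line therapy or prior osimertinib in the wrong descriptive table

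*SAP*

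**What the plan says.** Section 4.2.7 covers prior, concomitant and post-treatment medications. For those summaries, "incomplete medication or radiotherapy start and stop dates will be imputed as detailed in Section" 4.2.5.1. The three classes are then assigned from the imputed dates:

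- Prior: the stop date is before first dose.
- Concomitant: "Concomitant medications are those with a stop date on or after the first dose date of study treatment". A parenthesis adds that such medications may have begun before or during treatment.
- Post-treatment: the start date is after last dose.

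Section 4.2.5.1 gives date rules for diagnostic dates, adverse event starts, adverse event ends and partial death dates. It has none for medications. An adverse event start that lacks only its day is placed on the 1st of its month, or on the first-dose date if the two months coincide. With less known, the rules are "Missing day and month: impute 1st January unless year is the same as first dose date then impute first dose date" and, for a wholly absent start, "Completely missing: impute first dose date unless the end date suggests it could have started prior to this". An end that lacks only its day is placed at month end, or on the last-dose date if the two months coincide. With day and month missing, the end becomes 31 December, or last dose if the year is the same. The one plausibility check is "When imputing a start date ensure that the new imputed date is sensible e.g. is prior to the end date of the AE".

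**The concern.** For adverse events, moving starts towards first dose and ends towards the end of the month or year is cautious, because doubtful events are counted as on treatment. For anti-cancer therapies the order is often already known: a drug recorded as previous therapy came before study treatment, and one recorded as post-discontinuation therapy came after it. The borrowed rules ignore that knowledge and can overturn it.

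This matters more here than in most trials. The arms differ in osimertinib versus placebo, and Section 1.2 requires every patient to have progressed on earlier osimertinib. Section 4.2.7 records any treatment in the four weeks before study drug, which can include recently stopped osimertinib. An imputed date that makes osimertinib look concurrent with savolitinib plus placebo would read as exposure to the withheld component. In the other direction, next-line therapy missing from the post-treatment table weakens the context for overall survival. The arms are small: at the planned 28 per arm, which Section 1.3 says will not be met, one patient is 1/28 = 3.6%.

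**Working it through.** The SAP gives no figure on this point, so there is none to reproduce. The check applies the written rules. Let F be first dose and L be last dose.

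**Next-line start, incomplete**
- Month known, equal to the month of L: the start becomes the 1st of that month, or F if F is in the same month. Both are on or before L, so the record fails the post-treatment test. Its stop is after F and its imputed start is not after L, so it is concomitant even if the parenthesis is read as a limit.
- Year known, equal to the year of L: the start becomes F if F is in that year, otherwise 1 January. Both are on or before L, with the same result.
- Year known, later than the year of L: the start becomes 1 January of the later year, which is correctly post-treatment.

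**Prior osimertinib stop, incomplete**
- Month known, equal to the month of F: the stop becomes month end, or L if L is in that month. Both are on or after F, so the record is concomitant.
- Year known, equal to the year of F: the stop becomes 31 December, or L if L is in that year. Both are on or after F, so the record is concomitant.
- Year known, earlier than the year of F: the stop becomes 31 December of the earlier year, which is correctly prior.

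**Worked example** (illustrative dates: F = 20 March 2021, L = 10 September 2021)

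| True event | Known | Imputed | Class given |
|---|---|---|---|
| Osimertinib stop, 10 March | month | 31 March | concomitant |
| Osimertinib stop, 10 March | year | 10 September | concomitant throughout treatment |
| Next-line start, 25 September | month | 1 September | not post-treatment |
| Next-line start, 25 September | year | 20 March | not post-treatment |

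A next-line drug with a known start of 15 September and a stop known only as September gets a stop of 10 September, before it began. The plausibility check covers imputed starts only.

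**Overlap with complete dates.** A next-line drug taken from 25 September to 20 December 2021 starts after L, so it is post-treatment. It also stops after F, so it meets the concomitant stop-date test. Only a restrictive reading of the parenthesis keeps the two classes apart.

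**How often an incomplete record is misclassified.** The SAP does not give the gap g between osimertinib stop and first dose, or between last dose and next-line start. I assume 1 to 28 days, with first-dose dates spread evenly over two 365-day years (730 days, 24 months). For g up to 28:
- Day missing: the two dates share a month with share (730 − 24g)/730.
- Day and month missing: they share a year with share (730 − 2g)/730.

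| g (days) | Day missing | Day and month missing |
|---|---|---|
| 1 | 706/730 = 97% | 728/730 = 99.7% |
| 8 | 538/730 = 74% | 714/730 = 98% |
| 14 | 394/730 = 54% | 702/730 = 96% |
| 21 | 226/730 = 31% | 688/730 = 94% |
| 28 | 58/730 = 8% | 674/730 = 92% |

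Direct enumeration of the rules over 730 first-dose dates gave the same shares for both kinds of error, at assumed exposures of 60, 180 and 270 days.

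**The case against.** The best defence has four parts.

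- **The classes are already separated at source.** Table 2 and Section 4.2.6 list previous, concomitant and subsequent or post-discontinuation cancer therapy separately. This makes a false osimertinib entry less likely. However, Section 4.2.7 does not exempt those records from the imputation or the three definitions.
- **Leaning towards concomitant is the cautious convention.** This stands for ordinary medications and, in part, for prior osimertinib: forcing every partial stop to the day before first dose could hide real overlap. It does not justify removing next-line therapy from its own table.
- **There are safeguards.** Imputed starts must be sensible, imputations are flagged and all treatment data are listed, so a doubtful record can be traced. The one example of sensible compares a start with the event's own end, and an imputed next-line start passes it.
- **The parenthesis limits concomitant starts.** It can be read that way, so it would be wrong to say that the SAP has no start limit at all. It is worded as a permission, though, and both imputation errors occur under either reading.

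A reader might go further and infer effects on efficacy. Objective response and best response do exclude responses after subsequent therapy (Sections 3.2.1 and 3.2.5), but the imputation is expressly for medication and therapy summaries, and those sections do not draw on it. PFS and OS count events regardless of other therapy (Sections 3.2.2 and 3.2.4). Nor does the SAP say that the disallowed-medication summary is assigned from imputed dates.

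**Conclusion.** The defect is real but limited. The cross-reference leads to rules written for another data type, and as written they give wrong classes for identifiable records: starts or stops known only to the month or year of first or last dose. The categories can also overlap for fully dated next-line drugs.

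The effect is confined to descriptive medication and therapy summaries. The percentages above are conditional on a record being incomplete and on the assumed gap. It is tempting to read them as the share of patients misclassified, but the documents do not support that. The SAP gives no frequency of incomplete dates, which may be close to zero. Section 1.2 also admits patients who had osimertinib before chemotherapy, whose last osimertinib may lie well outside a 28-day gap.

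**What to change.** Replace the cross-reference in Section 4.2.7 with medication-specific rules:

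1. For therapies recorded as post-discontinuation cancer therapy, set an imputed start no earlier than the day after last dose of all study treatment.
2. Do not let an imputed stop precede a known start.
3. Define concomitant as a stop on or after first dose (or ongoing) and a start on or before last dose.
4. For therapies recorded as previous anti-cancer therapy whose partial stop date falls in the first-dose month or year, query the date. If it stays incomplete, report the therapy as prior, and flag and list it as possible overlap. Neither tabulate it as concomitant nor silently cap the date.

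The cost is a few sentences of SAP text, minor programming and one flagged listing. Apart from the date queries, no new data are needed. Item 4 leaves a small residue of records to be judged from the listing, which is preferable to a rule that either invents overlap or hides it.

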4.2.8 Pharmacokinetic data

Plasma concentrations of savolitinib, osimertinib and their metabolites (M2 and M3 for savolitinib; AZ5104 for osimertinib) will be summarised by nominal sample time using standard summary statistics for PK concentrations (geometric mean, geometric coefficient of variation, geometric mean \pm standard deviation, arithmetic mean, standard deviation, median, minimum, maximum and n) for the PK parameters listed in Section 3.4.

The time dependency of the PK on multiple dosing will be assessed by the calculation of the ratios of:

- C_{3h} Cycle 2 Day 1 / C_{3h} Cycle 1 Day 1
- $C_{pre-dose}$ Cycle 3 Day 1 / $C_{pre-dose}$ Cycle 2 Day 1
- $C_{pre-dose}$ Cycle 6 Day 1 / $C_{pre-dose}$ Cycle 2 Day 1

All plasma concentrations will be listed.

At Cycle 3 Day 1, PK parameters of C_{ssmax} , AUC_{ss} , T_{ssmax} , CL_{ss}/F for osimertinib, savolitinib and if appropriate for its metabolites, will be determined using non-compartment analysis by Covance PK alliance on behalf of AstraZeneca. Actual sample times will be used for the analysis.

Pharmacokinetic data will not be summarised by biomarker group.

4.2.9 Biomarkers

Biomarker endpoints will be analysed for the SAF.

The absolute change and the percentage change in EGFR mutation ctDNA allele frequencies at Week 6 will be summarised with descriptive statistics (n, mean, SD, median, min, max). Individual-level changes from baseline to all post-baseline timepoints will be summarised for

all patients. Waterfall plots of percentage change ctDNA allele frequencies at Week 6 will be included and spider plots of absolute and percentage changes in ctDNA allele frequencies over time may also be included.

The number and percentage of patients with detectable EGFR mutations at baseline and available data at 6-weeks, split by ctDNA clearance and non-clearance will be presented.

CCI

Other summaries and analyses for exploratory biomarkers may be documented in a separate analysis plan and will be reported in a separate report outside the CSR.

4.2.10 Analyses for cross-over patients

The assessment schedule for patients who cross-over will be determined by the point of cross-over, as described in Section 3.1.

Selected analyses will be repeated for the cross-over analysis set, including baseline characteristics, efficacy endpoints and safety analyses where sufficient data allow.

Any AE summary tables for cross-over patients will include all AEs that occurred after the start of cross-over treatment up until the end of the 28-day follow-up period. The 28-day follow-up period will be defined as the 28 days following discontinuation of treatment.

Cross-over analyses will not be presented by biomarker group.

5 INTERIM ANALYSES

Prior to CSP V3.0, a non-comparative interim futility analysis for the savolitinib plus placebo arm was planned to occur after 20 patients overall (10 per arm) had the opportunity to be treated for 2 RECIST post-baseline scans (12 weeks).

Under CSP V3.0, as a result of AstraZeneca's decision to terminate study recruitment early, the planned interim futility analysis will not be performed and there will be no requirement for data review by an external independent data monitoring committee (IDMC). Alternatively, following the termination of study recruitment, an initial DCO will occur to allow an early review of the data by AstraZeneca. The study will be unblinded after completion of data cleaning activities on the initial DCO data, and patients on savolitinib monotherapy (savolitinib plus placebo) will be given the opportunity to cross-over to the savolitinib plus osimertinib arm. If the investigator believes patients are gaining clinical benefit and patients have not reported PD, patients may continue to receive savolitinib monotherapy. All patients will be followed until the final analysis.

6 CHANGES OF ANALYSIS FROM PROTOCOL

The formula given in Section 3.5 for the percentage change in EGFR mutation ctDNA allele frequencies at week 6 and other time points will be $[\text{Week 6} - \text{baseline}] / \text{baseline} \times 100$, contrary to Section 9.4.5 of the CSP V3 which states it will be $[\text{Week 6 baseline}] / \text{baseline} \times 100$.

Previous versions of the SAP included comparative inferential analyses; however, since the SAP v2.0 update, it has been decided to remove all such analyses due to the lower than planned sample size following the CSP v3.0 amendment, with the exception of PFS and OS if there are at least 20 events. Where a comparative analysis was planned, summaries by treatment group will still be presented.

7 COUNTRY SPECIFIC ANALYSES

Not applicable.

9 APPENDICES

9.1 Important Protocol Deviations

Protocol deviations are collected, reviewed and reconciled throughout the study. Important protocol deviations (IPDs) are identified from the complete set of protocol deviations. IPDs are those which may significantly impact the reliability of the study data or that may significantly affect a patient's rights, safety, or wellbeing.

A set of pre-determined IPDs are listed in the protocol deviations plan. The protocol deviations plan also indicates which IPDs are identified by programmatic checks.

The IPDs are grouped into the following important protocol deviation (IPD) categories, where full details of the individual IPDs within each IPD category are provided in the protocol deviations plan:

- Inclusion and exclusion criteria deviations
- Discontinuation criteria for study product met but participant not withdrawn from study treatment
- Discontinuation criteria for overall study withdrawal met but participant not withdrawn from study
- IP deviation
- Excluded medications taken
- Deviations to study procedure
- Other important deviations.

The following general categories will be considered important protocol deviations (IPDs) and will be programmatically derived from Veeva Clinical Vault (VCV) data. These will be listed and summarised by randomised treatment group and discussed in the CSR as appropriate. Refer to the CSP for full details of the inclusion/exclusion criteria.

- Patients who deviate from key entry criteria per the CSP (Deviation 1)
 - Inclusion criteria 1, 2, 3, 4, 5, 6, 7, 8, 9, 10, 11, 12, 13, 15, 18
 - Exclusion criteria 3, 7, 11, 12, 13, 16, 17, 21, 23
- Discontinuation criteria for study product met but participant not withdrawn from study treatment (Deviation 2)
- Discontinuation criteria for overall study withdrawal met but participant not withdrawn from study (Deviation 3)
- Investigational product deviation (Deviation 4)
- Excluded medications taken (Deviation 5)
- Baseline RECIST > 42 days before date of randomisation (Deviation 6)
- No baseline RECIST assessment on or before date of randomisation (Deviation 7)
- Other important deviations (Deviation 8)

- Patients randomised but who did not receive study treatment (Deviation 9).

10 DOCUMENT REVISION HISTORY

Version	Description of Update
1.0	First approved SAP version.
1.3	
The following changes have been made to version 1:
 
 (i) Signature pages have been removed, since signatures will be collected electronically. (ii) List of abbreviations has been updated, and abbreviations have been spelled out in full on first mention throughout. (iii) Section 2.1 Definition of Analysis Sets – More detail has been added to the definition of the PK analysis set. (iv) Section 3.1.1 Target lesions (TLs) – Site investigator data has been updated to add text related to RECIST in non-registration studies about scaling up missing sum of TL when there are $\leq 1/3$ missing. (v) Section 3.5 Biomarker variables – The formula for percentage change in EGFR ctDNA allele frequencies at week 6 and other time points was corrected, and will be $[\text{Week } 6 - \text{baseline}]/\text{baseline} \times 100$. (vi) Section 4.2 Analysis Methods – In Table 6, clarification has been added that the profile likelihood confidence interval will be calculated for PFS. (vii) Section 4.2.2.1 Objective response rate (ORR) – More detail has been added about the use of the Cochran-Mantel-Haenszel test, and on summaries of the ORR presented by treatment group. (viii) Section 4.2.2.1.2 Subgroup analyses – has been updated to include subgroup analysis by FISH allocation status. (ix) Section 4.2.3.4 Change in TL tumour size – In the description of the ANCOVA models for absolute and percentage change in TL tumour size, the term “the absolute (percentage) change in week 12 value” has been removed, since this would not be a covariate in the models. (x) Section 4.2.5.1 General considerations for safety assessments – has been updated with the following: 
 a. The visit windows for vital signs data: Day 15 and Day 22 had incorrect upper and lower limits. b. Details regarding vital signs schedule in brackets were removed.

Version	Description of Update
	
c. A bullet point describing summaries at patient levels was removed, since this was partially a repeat of a previous point, and did not make sense as we would not present a summary at patient level.
 
d. A point was added to clarify that adverse events occurring in the savolitinib + placebo group will be split into two presentations, depending on whether they occurred before or after cross-over.
 
(xi) Section 4.2.5.2 Adverse events (AEs) – has been updated with the following:
 
a. Summaries of AEs with CTCAE grade 3 or 4 have been changed to grade 3 or higher.
 
b. Most common AEs are defined as occurring in at least 10% of patients, changed from at least 5%.
 
(xii) Section 4.2.5.3 Adverse events of special interest (AESI) – This section has been added.
 
(xiii) Section 4.2.5.4 Vital signs – This section has been added.
 
(xiv) Section 4.2.5.5 Laboratory summaries – This section has been added.
 
(xv) Section 4.2.5.6 Electrocardiograms (ECGs) – This section has been added.
 
(xvi) Section 4.2.5.7 Multi-gated Acquisition (MUGA)/Echocardiogram (ECHO) – This section has been added.
 
(xvii) Section 4.2.5.8 Exposure – This has been updated as follows:
 
a. The bullet “Summary of duration of exposure of savolitinib and osimertinib” has been removed since this is a duplicate, and the first bullet has been changed to “Total exposure and actual exposure of savolitinib and osimertinib” for clarification.
 
b. Summary of dose delays have been removed, as these are not applicable to this study.
 
c. Cumulative exposure over time showing the number and percentage of patients treated for at least 0, 6 and 12 months was added.
 
(xviii) Section 4.2.8 Pharmacokinetic data – Median has been added to the list of summary statistics for PK parameters.
 
(xix) Section 4.2.10 Analyses for cross-over patients – This has been updated as follows:
 
a. To remove ambiguity about analysis of OS, which may only be repeated if there are sufficient events.

Version	Description of Update
	
b. Added summaries of exposure and ECHO data.
 
(xx) Clarified that ctDNA and PK parameter analyses may only be repeated if there are sufficient data. Section 6 Changes of Analysis from Protocol – This has been updated to reflect changes in Sections 3.5 and 4.2.3.4 that are inconsistent with the protocol.
 
(xxi) Section 9.1 Important Protocol Deviations – This has been updated to provide a summary and refer to the protocol deviations plan.

2.0	
The following changes have been made following early termination of study recruitment and under CSP v3.0:
 
(i) Section 1.2 Study Design – Updated to reflect early termination of study recruitment and its impact on crossover procedures and removal of futility analysis.
 
(ii) Section 1.3 Number of patients – Updated to clarify the planned sample size will not be met.
 
(iii) Section 2.1 Definition of Analysis Sets:
 
a. Added that patients will be assigned to analysis sets prior to analyses being performed
 
b. Changed Safety analysis set abbreviation from SAS to SAF
 
c. Added Monotherapy analysis set, and explained the interim futility analysis set is no longer required.
 
d. Table 2: Additional column flagging variables to be summarised by biomarker groups, and removal of interim futility analysis. Simplified cross-over analysis variables.
 
(iv) Section 3.1 Derivation of RECIST Visit Responses – Amended scheduled assessments details for patients who cross-over.
 
(v) Section 3.1.4 Independent review – Amended to state BICR will no longer be performed.
 
(vi) Section 3.2.1 Objective response rate – Removed ORR defined using BICR data.
 
(vii) Section 3.2.2 Progression free survival:
 
a. Amended definition of two missed visits and added Table 6.
 
b. Removed RECIST rules applying to BICR assessments.

Version	Description of Update
	
(viii) Section 3.2.5 Best objective response – Removed derivation using BICR data.
 
(ix) Section 3.2.6 Change in TL tumour size – Added details of imputation for percentage change at week 12.
 
(x) Section 3.4 Pharmacokinetic variables – Removed Cycle 11 Day 1 from summarised data.
 
(xi) Section 3.5 Biomarker variables – Added sub-headings for secondary and exploratory variables, and definitions of biomarker groups (FISH10+ and CCI).
 
(xii) Section 4.1 General Principles:
 
 a. Added definitions of biomarker groups and presentation of analyses by both biomarker and treatment group. b. Removed paragraph about stratification, since this applied to comparative analyses which will no longer be done. 
(xiii) Section 4.2 Analysis Methods – Removed Table 7 since comparative/ formal statistical analysis will no longer be done.
 
(xiv) Section 4.2.1 Multiplicity – Amended to state there will be no adjustment for multiplicity.
 
(xv) Section 4.2.2.1 Objective response rate:
 
 a. Removed sentence about summaries per BICR. b. Removed all comparative/inferential analyses. c. Added summary of ORR in monotherapy analysis set. d. Added repeat of ORR analysis and BoR analysis for patients in second line patients. 
(xvi) Section 4.2.2.1.1 ORR sensitivity analyses – Section removed.
 
(xvii) Section 4.2.2.1.1 Subgroup analyses:
 
 a. Clarified that values for prior lines of therapy will come from IWRS b. Added explanation of FISH allocation status (moved from section 3.5) c. Removed logistic regression modelling and all mention of comparative analyses.

Version	Description of Update
	
d. Added repeat of subgroup analysis for biomarker groups.
 
(xviii) Section 4.2.3.1 Progression free survival:
 
a. Removed all comparative/inferential analyses.
 
b. Added repeat of PFS analysis and KM plots of PFS for patients in second line patients.
 
(xix) Section 4.2.3.1.1 PFS sensitivity analyses – Section removed.
 
(xx) Section 4.2.3.2 Duration of response – Added repeat of DoR analysis and KM plot for patients in second line patients.
 
(xxi) Section 4.2.3.3 Overall survival – Removed bullet point and combined with paragraph above.
 
(xxii) Section 4.2.3.4 Change in TL tumour size:
 
a. Removed all comparative/inferential analyses.
 
b. Added repeats of waterfall and spider plots in second line patients.
 
(xxiii) Section 4.2.4 Data cut-offs – Amended so originally planned futility, primary and final analyses will no longer take place, and instead that under CSP v3.0 there will be an initial DCO for early data review and a final DCO after all patients have had a 9 month follow-up.
 
(xxiv) Section 4.2.5.2 Adverse events:
 
a. Amended so summary information will be tabulated by treatment group (not savolitinib or osimertinib or the combination).
 
b. Added definition of treatment emergent.
 
(xxv) Section 4.2.6 Demographic and baseline characteristics – Amended age groups, and added to disease characteristics at baseline.
 
(xxvi) Section 4.2.8 Pharmacokinetic data – Removed calculation of ratio of $C_{pre-dose}$ Cycle 11 Day 1 / $C_{pre-dose}$ Cycle 2 Day 1 since Cycle 11 due to removal of requirement for PK sample collection at Cycle 11. Clarified this will not be summarised by biomarker group.
 
(xxvii) Section 4.2.10 Analyses for cross-over patients:
 
a. Referred to Section 3.1 for assessment schedule

Version	Description of Update
	
 b. Simplified to say selected analyses will be repeated for these patients, including baseline, efficacy and safety. c. Clarification that cross-over analysis will not be repeated by biomarker groups. 
(xxviii) Section 5 Interim Analyses – Removal of interim analysis with explanation that it is no longer required under CSP V3.0.
 
(xxix) Section 6 Changes of Analysis from Protocol:
 
 a. Noted the removal of comparative analyses from the study due to low sample size. b. Noted the removal of BICR. c. Removed the change previously noted relating to ANCOVA models, since this is now redundant. 
(xxx) Section 9.1 Important Protocol Deviations – List amended in line with updated non-compliance handling plan v3, and TA SAP.

3.0	
The following changes have been made following the decision to reintroduce the BICR and associated analyses, and some comparative analyses:
 
 (i) Section 3.1.4 Independent review – Reverted back to text from v1.3 which states a planned blinded independent central review (BICR) will be carried out. (ii) Section 3.2.1 Objective response rate – Reverted back to text from v1.3 which includes sentence about BICR data. (iii) Section 3.2.2 Progression free survival – Reverted back to text from v1.3 regarding rules applying to BICR assessments. (iv) Section 3.2.5 Best objective response – Reverted back to text from v1.3 which includes derivation using BICR data. (v) Section 4.1 General Principles – Re-inserted sentence on stratification variables source to be used. (vi) Section 4.2.2.1 Objective response rate – Added back sentence from v1.3 about summaries per BICR data, and text originally from an ORR sensitivity analysis section describing how disagreements will be presented (vii) Section 4.2.3.1. Progression free survival (PFS): 
 a. Re-inserted text from v1.3 describing estimation of HR and its corresponding CI, with added clarification that this will only be done if there are ≥ 20 events. Similarly, this will be repeated for second line patients and per BICR if there are ≥ 20 events. b. Added back sentence from v1.3 about summaries per BICR data, and text originally from a PFS sensitivity analysis section describing how disagreements will be presented.

Version	Description of Update
